6.2.2 On-Study Evaluations

Evaluations during the MVC treatment intensification period will occur on weeks 2, 4, 8, 12, and 24. An addition visit will occur after MVC treatment intensification on week 36. Study visits at week 2 and 4 will have a visit window period of 1 week. For study visits at week 8, 12, 24 and 36 there will be a 2 week visit window period. In instances of virologic failure and/or premature treatment discontinuation evaluations would also need to occur as soon as possible.

Total blood volume for laboratory evaluations during MVC treatment intensification (week 2 to week 24) will be approximately 200 mL.

Lumbar puncture – 25 mL cerebral spinal fluid (week 4 and 24)

Total blood volume for laboratory evaluations during post-MVC treatment intensification (week 36) will be approximately 40 mL.

6.2.3 Evaluations and plan for registered subjects that do not complete week 4 of the study:

- a. Those subjects that do not start treatment will be replaced and will have no follow-up evaluations performed.
- b. Subjects that discontinue antiretroviral therapy and/or MVC before week 4 will be replaced and will have no follow-up evaluations performed.

6.2.4 Evaluations and plan for randomized or registered subjects that complete week 4 but not the remainder of the study:

- a. Subjects who complete week 4 of the study but then discontinue their antiretroviral regimen and/or MVC will not be replaced and will not be discontinued from the study.

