6.3.6 Clinical Assessments

Complete Physical Exam

A complete physical examination will be performed at entry. Documentation must include a complete review of systems and any HIV-related, toxicity-related, or AIDS-defining events.

Targeted Physical Exam

A targeted physical examination will be based on any signs or symptoms previously identified that the subject has experienced within 30 days of entry or since the last visit. This examination will be performed at entry, weeks 12, 24 and 36 and in instances of virologic failure or premature treatment discontinuation if they should occur. Documentation must include any HIV-related, toxicity-related, or AIDS-defining events.

Height and Weight

Height and weight should be measured at study entry.

Signs and Symptoms

All signs, symptoms, deaths, and toxicities must be documented in the subject's record. At entry, record all signs/symptoms experienced within 30 days of entry on the CRFs. For all other visits including the time of confirmation of virologic failure, record all Grade ≥ 2 signs and symptoms, HIV-related and AIDS-defining events and deaths on the CRFs that have occurred since the last visit. Any signs or symptoms that lead to a change in treatment, regardless of Grade, must be recorded on the CRF. The source document must include date of onset and date of resolution, but the CRF will only record prevalence of a given adverse event since the previous study visit.

Refer to the Division of AIDS Table for Grading Adult Adverse Experiences, which can be found on the CCTG website: www.cctg.ucsd.edu

Diagnoses

The following should be recorded on the CRFs: HIV-related diagnoses, HIV-related malignancies, non-HIV related malignancies, myocardial infarctions,

hepatic failures, AIDS-defining events and death. Any other diagnosis that is, in the opinion of the site investigator, associated with study medications, should be recorded on the adverse event CRF. The source document must include date of diagnosis and date of resolution.

Karnofsky Performance Status

A Karnofsky performance status must be completed within 30 days before study entry.

Vital Signs

Temperature, pulse, and blood pressure collected at all visits and kept as a part of the source document.

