5. Association between change in early immune subsets and phase 2 CD4 recovery will be assessed via Pearson's correlation analysis.

6. MVC plasma to CSF ratios at weeks 4 and 24 will be reported via descriptive statistics. Differences in MVC concentration ratios between subjects receiving a PI/r- vs. NNRTI-based background regimen will be compared via McNemar's test or paired t-tests as appropriate.

7. Descriptive statistics of CNS markers of immune activation will be reported via descriptive statistics. Differences in CNS markers of immune activation between baseline and weeks 4 and 24 will be compared cross-sectionally via McNemar's test or paired t-tests as appropriate.

8. Association between change in CNS markers of immune activation and MVC plasma to CSF ratios will be assessed via Pearson's correlation analysis.

9. Descriptive statistics of toxicity/intolerance during MVC treatment intensification will be reported via descriptive statistics. Differences in proportions of grades > 2 laboratory abnormalities and signs and symptoms will be compared via McNemar's test between time points.

10. Virologic failure during MVC treatment intensification will be reported via descriptive statistics.

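### McNemar's test on signs and symptoms between unnamed visits mixes recording-window length with drug effect wherever the two windows differ, as at entry versus week 24

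*Combined protocol and SAP*

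**What the plan says.** Item 9 of section 9.4.3.1 (Analysis of Secondary Objectives) first promises a descriptive summary of toxicity during maraviroc (MVC) intensification, then adds a test: "Differences in proportions of grades > 2 laboratory abnormalities and signs and symptoms will be compared via McNemar's test between time points". It does not say which time points, and it sets no common recording window and no exposure adjustment.

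Section 6.3.6 (Clinical Assessments) fixes the windows. At the start: "At entry, record all signs/symptoms experienced within 30 days of entry on the CRFs". Later: "For all other visits including the time of confirmation of virologic failure, record all Grade ≥ 2 signs and symptoms", counted from the last visit. On what reaches the database: "the CRF will only record prevalence of a given adverse event since the previous study visit". Dates are kept elsewhere: "The source document must include date of onset and date of resolution".

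Section 6.2.2 gives the visits: "Evaluations during the MVC treatment intensification period will occur on weeks 2, 4, 8, 12, and 24", with one more at week 36. On tolerance it says "Study visits at week 2 and 4 will have a visit window period of 1 week" and "For study visits at week 8, 12, 24 and 36 there will be a 2 week visit window period".

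On the grade threshold, endpoint 3 in section 9.2.2 and the recording rules in 6.3.6 and 6.3.7 use grade 2 or higher. Objective 1.2.4 and item 9 print a strict greater-than sign.

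**The concern.** McNemar's test asks whether two paired proportions are equal. For a symptom recorded as present at any time in a window, the proportion grows with the length of the window. If one window is 2.8 times the other, the null hypothesis is false even when the drug does nothing.

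Section 9.4.3.1 frames its secondary tests as before-and-after comparisons, so entry against an on-drug visit is a natural choice, and entry versus week 24 is one of the unequal pairs. With no control arm, a significant rise there could be read as drug toxicity. An early comparison can err the other way: with a 10% risk over 30 days at entry, a true doubling of the rate seen over only 14 days gives 1 - 0.90^(2 × 14/30) = 9.4%, which looks like no change. Objective 1.2.4 asks for a rate, and this test does not estimate one.

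**Working it through.** The plan states no error rate or power for item 9, so there is no figure to reproduce.

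**Windows** (6.2.2 and 6.3.6; differences between visit weeks × 7)

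| Visit | Entry | Wk 2 | Wk 4 | Wk 8 | Wk 12 | Wk 24 | Wk 36 |
|---|---|---|---|---|---|---|---|
| Look-back, days | 30 | 14 | 14 | 28 | 28 | 84 | 84 |

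With weeks 12 and 24 each allowed 2 weeks either way, the week 24 look-back runs from 84 - 28 = 56 to 84 + 28 = 112 days.

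The nominal windows are equal for weeks 2 vs 4, 8 vs 12 and 24 vs 36, and nearly equal for entry vs week 8 or 12 (30 vs 28). They are clearly unequal for entry vs week 24 (84/30 = 2.8-fold), week 4 vs week 24 (84/14 = 6-fold) and entry vs week 4 (14/30 = 0.47).

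**Assumptions.** The outcome is any grade 2 or higher symptom. The rate is constant with no drug effect, windows are independent within a subject, there are 30 complete pairs, and the test is exact, two-sided, at 0.05 (the plan says two-sided but gives no alpha). The 30-day risk p is varied because the documents give none.

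**Formulas.** The risk over d days is 1 - (1 - p)^(d/30). With risks p1 and p2 in the two windows, a pair is discordant upwards with probability p2(1 - p1) and downwards with p1(1 - p2). The number of discordant pairs is binomial(30, sum of the two). Given that number, the upward count is binomial with the upward share. Rejections are summed by direction; nominal is at most 2.5% each way. At least 6 discordant pairs are needed (all one way: 2 × 0.5^6 = 0.031; with 5, 0.0625).

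**Worked case, entry vs week 24, p = 10%.** The week 24 risk is 1 - 0.90^2.8 = 25.5%. Upward discordance is 0.2555 × 0.90 = 0.230 and downward is 0.10 × 0.7445 = 0.074. The false-increase probability is 22%.

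**False significant increase, entry vs week 24**

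| 30-day risk | 2% | 3% | 5% | 10% | 20% |
|---|---|---|---|---|---|
| Risk over 84 days | 5.5% | 8.2% | 13.4% | 25.5% | 46.5% |
| 84 days, 30 pairs | 0.3% | 1.4% | 6.5% | 22% | 48% |
| 84 days, 25 pairs | 0.1% | 0.7% | 3.8% | 17% | 38% |
| All at 56 days, 30 pairs | 0.04% | 0.2% | 1.4% | 6.3% | 15% |
| All at 112 days, 30 pairs | 1.1% | 4.6% | 16% | 44% | 77% |

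The last two rows are limits, with every subject at the edge of the tolerance. With 30 pairs the false-increase rate passes 2.5% at a 30-day risk of 3.5% (84 days), 6.3% (56 days) or 2.5% (112 days).

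**Other pairs, 30 pairs, risks of 5%, 10% and 20%**
- Week 4 vs week 24, false increase: 12%, 47%, 84%.
- Entry vs week 4, false decrease: 0.2%, 2.1%, 9.8%.

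**Relaxing independence (84 days)**
- If 20% of subjects have a persistent symptom counted in both windows, discordant probabilities are multiplied by 0.80. The false increase becomes 3.4%, 15% and 36% at 5%, 10% and 20%.
- With gamma variation in rates between subjects (variance 1, simulated), it is 18% and 36% at average 30-day risks of 9.5% and 18.2%.

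**After the fix (same model, 5%, 10%, 20%)**
- 28 vs 28 days: 0.1%, 0.5%, 1.1% in each direction.
- Weeks 2 and 4 pooled (28 days) vs 30 days: false increase 0.1%, 0.4%, 0.8%; false decrease 0.1%, 0.6%, 1.4%. At the tolerance limits and 20% risk: 2.2% increase (35 days) and 3.8% decrease (21 days).

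**The case against.** The strongest reply is that item 9 does not commit to an affected pair. Baseline against weeks 4 and 24 is named in item 4, for flow-cytometry markers drawn only at those visits. Symptoms are assessed at every visit from entry on. Week 24 against week 36, on versus off drug, is a sensible safety contrast with nominally equal windows. This stands: the affected pairs are an inference, and a reader who concludes that every comparison under item 9 is biased goes further than the text allows.

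Second, the size depends on the outcome. Section 6.3.6 speaks of a given adverse event, so symptom-by-symptom testing is as plausible as an any-symptom composite. At 1%, 2% and 3% risk per symptom the false-increase rate is 0.01%, 0.3% and 1.4%, all below nominal. If item 9 really means grades above 2, events are presumably rarer still. This also stands.

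Third, 30 pairs is a ceiling, since section 7 removes some subjects with toxicity from the study. With 25 pairs the figures fall but remain above nominal at 5% risk and higher.

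Fourth, a reader might infer that entry versus week 4 would regularly produce false reassurance. As a significance result it does not: the false-decrease rate is within 2.5% at 5% and 10% risk and exceeds it only at the assumed 20%.

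Fifth, the threshold mismatch could be read as a firm contradiction. The strict sign may be an underlined symbol lost when the text was extracted, so it needs a check and cannot be called a proven error.

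None of this equalises the windows. The plan leaves the choice of pair open, and for the unequal pairs the null hypothesis is wrong by construction.

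**Conclusion.** The concern holds for pairs of visits with clearly unequal symptom windows, chiefly entry or week 4 against week 24. There, a difference in proportions cannot be attributed to MVC. For an any-symptom grade 2 or higher outcome with 30-day risks of 5% to 20%, the false-increase rate for entry versus week 24 is 6.5% to 48% with 30 complete pairs and 3.8% to 38% with 25, against a nominal 2.5%. These figures rest on assumed risks, a constant rate, independent windows and the nominal 84 days. Below about 3.5% risk with 30 pairs there is no inflation, so rare single symptoms and grade 3-4 events are not a practical problem.

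Laboratory grades from visit draws and item 9's descriptive summary are outside the point. A reader might infer that the trial's safety conclusions are unsound. The documents do not support that: this is an unadjusted secondary test in a single-arm pilot, and safety decisions rest on the adverse event and monthly toxicity reports and the review trigger in section 9.5. Severity is minor.

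**What to change.** 1. For signs and symptoms, replace the visit-to-visit test with new-onset events per person-time in three periods: the 30 days before entry, time on MVC, and time off MVC to week 36. Give rate ratios with confidence intervals clustered on subject. At a constant rate the expected event rate is the same in each period, whatever its length.
2. If McNemar's test is preferred, use equal windows lying wholly on one side of the first dose. For the late contrast, compare the last 28 days before entry with the last 28 days before the week 24 visit, using source onset and resolution dates. For the early contrast, pool weeks 2 and 4 (about 28 days; 21 to 35 with visit tolerance) against the 30 days before entry. Do not apply a 30-day look-back at week 4: it reaches day -2 (day -9 for a permitted day 21 visit), so it includes pre-drug days and overlaps the entry window.
3. Keep McNemar's test for laboratory grades at named visits, and name the visits for every comparison in item 9.
4. Use the endpoint's grade 2 or higher threshold in objective 1.2.4, section 9.2.2 and item 9, after checking the printed sign in the source file.

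Naming visits and pooling weeks 2 and 4 need only SAP wording. Person-time rates and the 28-day windows need dates that the source documents must already hold, so they cost added date entry on the CRF or one abstraction for about 30 subjects. The threshold is a short protocol clarification. No visits or samples are added.

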9.5 Monitoring

The safety and tolerability of the study medications will be monitored by means of adverse event reports (AER) and monthly toxicity reports that will include laboratory and clinical data. These reports will be discussed by the protocol team on monthly conference calls.

Data and Safety Monitoring Board, it is the responsibility of the Principal Investigator and the CCTG protocol team to interpret the toxicity data and make any decisions needed to protect patients from undue risk. Accrual and toxicity summaries will be provided to the Protocol Chairs and CCTG Investigators by the Data Manager and Biostatistician.

If more than **five** patients develop virologic failure or discontinue MVC due to an adverse event or laboratory toxicity, an independent interim review committee will be established to review the study results to date. The interim review committee will be composed of at least 3 people (including one statistician) outside the protocol team. The committee will make specific recommendations about changes to the study protocol.

10.0 DATA COLLECTION AND MONITORING AND ADVERSE EXPERIENCE REPORTING

10.1 Records to Be Kept

Case report forms (CRF) will be provided for each subject. Subjects must not be identified by name on any CRFs. Subjects will be identified by the patient identification number (PID) provided by the CCTG Data Unit upon registration.

10.2 Role of Data Management

10.2.1 Instructions concerning the recording of study data on CRFs will be provided by the CCTG Data Unit.

10.2.2 It is the responsibility of the CCTG Data Unit to assure the quality of computerized data for this study.

10.3 Clinical Site Monitoring and Record Availability

10.3.1 Site monitors provided by the CCTG will visit participating clinical research sites to review the individual subject records, including consent forms, CRFs, supporting data, laboratory specimen records, and medical records (physicians' progress notes, nurses' notes, individuals' hospital charts), to ensure protection of study subjects, compliance with the protocol, and accuracy and completeness of records. The monitors also will inspect sites' regulatory files to ensure that regulatory requirements are being followed and sites' pharmacies to review product storage and management.

10.3.2 The investigator will make study documents (e.g., consent forms, drug distribution forms, CRFs) and pertinent hospital or clinic records readily available for inspection by the local IRB, the site monitors, the Food and Drug Administration (FDA), the pharmaceutical sponsor(s), or the sponsor's designee for confirmation of the study data.

10.4 Serious Adverse Experience (SAE) Reporting

Serious adverse experiences must be documented on the Serious Adverse Experience (SAE) Reporting Form and submitted to the CCTG Data Unit.

11.0 HUMAN SUBJECTS

11.1 Institutional Review Board (IRB) Review and Informed Consent

This protocol and the informed consent document and any subsequent modifications will be reviewed and approved by the IRB or ethics committee responsible for oversight of the study. A signed consent form will be obtained from the subject. The consent form will describe the purpose of the study, the procedures to be followed, and the risks and benefits of participation. A copy of the consent form will be given to the subject.

11.2 Subject Confidentiality

All laboratory specimens, evaluation forms, reports, and other records that leave the site will be identified by coded number only to maintain subject confidentiality. All records will be kept locked. All computer entry and networking programs will be done with coded numbers only. Clinical information will not be released without written permission of the subject, except as necessary for monitoring by IRB, the FDA, the OHRP, the pharmaceutical supporter(s), or the supporter's designee.

11.3 Study Discontinuation

The study may be discontinued at any time by the IRB, the pharmaceutical supporter(s), the FDA, or other government agencies as part of their duties to ensure that research subjects are protected.

12.0 PUBLICATION OF RESEARCH FINDINGS

Publication of the results of this trial will be governed by CCTG policies. Any presentation, abstract, or manuscript will be made available for review by the pharmaceutical supporters prior to submission.

13.0 BIOHAZARD CONTAINMENT

As the transmission of HIV and other blood-borne pathogens can occur through contact with contaminated needles, blood, and blood products, appropriate blood and secretion precautions will be employed by all personnel in the drawing of blood and shipping and handling of all specimens for this study, as currently recommended by the Centers for Disease Control and Prevention and the National Institutes of Health.

All infectious specimens will be transported using packaging mandated in the Federal Code of Regulations, CDC 42 CFR Part 72. Please also refer to individual carrier guidelines, e.g., FedEx, Airborne, for specific instructions.

